### **5.9.1.2 Analysis of primary and secondary outcome measures**

Only the first occurrence of the event after the index date will be counted in analyses. For both the IV LCM group and comparator group, counts and frequency of events will be recorded. For both the IV LCM high dose group and comparator group, several incidence rates will be calculated. First, the overall incidence rate of any event of interest will be calculated. Second, incidence rates for each of the following events will be calculated individually: Cardiac disorders, Skin and subcutaneous tissue disorders, Nervous system disorders, Metabolism and nutrition disorders, Psychiatric disorders, Injury, poisoning and procedural complications, General disorders and administration site conditions, and Investigations, Drug reaction with eosinophilia and systemic symptoms syndrome, Severe cutaneous adverse reactions and Hypersensitivity events. Third, incidence rates for each subcategory of the abovementioned events and associated 95% confidence intervals will be calculated. The incidence rate of each event with associated 95% confidence interval will be calculated for the IV LCM high dose group and comparator group.

The numerator will be the total number of patients with the outcomes identified during the follow-up period. The denominator will be in patient-days. That is, the total summation of individual patient-days at risk up to the first occurrence of the AE of interest for subjects with

that AE, and the total patient-days at risk calculated up to the censoring date i.e. discontinuation of IV LCM plus 30 days or loss to follow-up for those subjects not experiencing that AE. Incidence rates will be presented with a 95% exact confidence interval based upon the Poisson distribution or another relevant model if there is nonconvergence. It is important to note incidence rates per time at risk are based on a constancy assumption. That is, the rates per unit of time assume that the event occurs with a constant rate over time. Events that are more likely to occur early or late relative to the initial exposure or with an increasing or decreasing hazard rate over time would not meet the constancy assumption and these rates should be viewed with caution. The person time for each patient will be calculated as the total number of days of follow-up as described in Section 5.3.3 .

Incidence rate ratios associated 95% confidence intervals will be calculated for each outcome to compare the incidence rates of the AEs for the IV LCM high dose group to those for the comparator group.

Those with SE will have the same data presented in separate tables as well as contributing to the main results.

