## 4 RESEARCH QUESTION AND OBJECTIVES

The primary objective of this study is to estimate the incidence of the select medical events of interest, those being the 8 System Organ Classes (SOCs) and 3 Standardized MedDRA Queries (SMQs) listed below, in pediatric patients after treatment with higher IV LCM doses, compared to pediatric patients treated with recommended initial/maintenance IV LCM dose:

- Cardiac disorders

- 
- Skin and subcutaneous tissue disorders
  - Nervous system disorders
  - Metabolism and nutrition disorders
  - Psychiatric disorders
  - Injury, poisoning and procedural complications
  - General disorders and administration site conditions
  - Investigations of ECG indicating long PR
  - Drug reaction with eosinophilia and systemic symptoms syndrome
  - Severe cutaneous adverse reactions
  - Hypersensitivity

The secondary objectives of this study are:

1. To estimate the incidence of the selected medical events included in the 8 System Organ Classes (SOC) and 3 Standardized MedDRA Queries (SMQs) as indicated below, in pediatric patients after treatment with higher than the recommended IV LCM doses, compared to pediatric patients treated with recommended initial/maintenance IV LCM dose.
- Cardiac disorders
    - Atrioventricular block
    - Atrioventricular block complete
    - Atrioventricular block first degree
    - Atrioventricular block second degree
    - Arrhythmia
    - Bradyarrhythmia
    - Bradycardia
    - Cardiac fibrillation
    - Cardiac flutter
    - Tachyarrhythmia
    - Atrial fibrillation
    - Atrial flutter
    - Cardiac arrest
    - Torsade de pointes
    - Ventricular arrhythmia
    - Ventricular fibrillation
    - Ventricular tachyarrhythmia
    - Palpitations
  - Skin and subcutaneous tissue disorders
    - Stevens-Johnson syndrome
    - Toxic epidermal necrolysis
    - Angioedema
    - Urticaria

- Pruritus
  - Rash
  - Nervous system disorders
    - Dizziness
    - Somnolence
    - Paresthesias
    - Loss of consciousness
    - Syncope
  - Metabolism and nutrition disorders
    - Appetite disorder
    - Decreased appetite
    - Diet refusal
    - Hypophagia
    - Food aversion
  - General disorders and administration site conditions
    - Chest pain
    - Gait disturbances
  - Injury, poisoning and procedural complication
    - Injection site discomfort
    - Injection site erythema
    - Injection site irritation
    - Injection site pain

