### 5.3.3 Follow-up (post-index) period

The duration of follow-up is for a maximum of 37 days from index date.

IV LCM treatment may span several days; treatment will be considered continuous if subsequent IV LCM treatment is noted to occur within 7 days of a previous treatment. If 7 days pass without a documented iv or LCM treatment, the index exposure has ended. Follow then continues until end of follow up or until the following censoring conditions apply:

Censoring: Patients will be followed for either 37 days OR until the patient is lost to follow-up[transfer out]; OR the patient is discharged from the in-patient setting [events that occur at home are not easy to track and are not included here; outpatient setting events are also excluded as we do not know what the patient has been doing at home during routine care]; OR the patient dies; OR the patient switches to another AED instead of/or adjunct to LCM; whichever comes first.

Clarification of follow up: The purpose of the study is to evaluate iv loading dose and higher subsequent dosing risk. Some patients may receive only one iv loading dose and then transfer to oral dosing which may last some weeks in the hospital setting. In the case where a patient has just one dose of iv LCM and switches to continuous oral LCM therapy, the follow up for AE evaluation will cease after a maximum of seven days of oral therapy or until censoring occurs as above. The same applies for those exposed to one dose of iv LCM and no further LCM exposure (either oral or iv).

Patients who have more than one dose of iv LCM and then switch to oral therapy will have a maximum follow up of 37 days of follow up index date or until censoring.

Patient time is contributed until either end of follow up or censor point (in days).

Patients are only included once in this study, so if we find evidence of a further iv loading dose of LCM given 6 months later say, they do not contribute to the study.

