## **5.5 Variables**

### **5.5.1 Primary outcome measure**

The following primary variables will be measured to meet the study objectives:

- The incidence rate and incidence rate ratio of cardiac disorders (selected preferred terms (PTs) as described in Section 5.5.5)
- The incidence rate and incidence rate ratio of general disorders and administration site conditions (selected PTs as described in Section 5.5.5)
- The incidence rate and incidence rate ratio of injury, poisoning and procedural complications (selected PTs as described in Section 5.5.5)
- The incidence rate and incidence rate ratio of investigations (i.e. the incidence rate of ECG PR prolongation)
- The incidence rate and incidence rate ratio of skin and subcutaneous tissue disorders (selected PTs as described in Section 5.5.5)
- The incidence rate and incidence rate ratio of drug reactions with eosinophilia and systemic symptoms syndrome (selected PTs as described in Section 5.5.5)
- The incidence rate and incidence rate ratio of severe cutaneous adverse reactions (selected PTs as described in Section 5.5.5)
- The incidence rate and incidence rate ratio of hypersensitivity (selected PTs as described in Section 5.5.5)
- The incidence rate and incidence rate ratio of nervous system disorders (selected PTs as described in Section 5.5.5)
- The incidence rate and incidence rate ratio of metabolism and nutrition disorders (selected PTs as described in Section 5.5.5)

- The incidence rate and incidence rate ratio of psychiatric disorders (i.e. abnormal behavior)

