### **5.5.2 Secondary outcome measure**

The secondary variables that will be evaluated in this study include:

- Incidence rate and incidence rate ratio of atrioventricular block
- incidence rate and incidence rate ratio of atrioventricular block complete
- incidence rate and incidence rate ratio of atrioventricular block first degree
- incidence rate and incidence rate ratio of atrioventricular block second degree
- incidence rate and incidence rate ratio of arrhythmia
- incidence rate and incidence rate ratio of bradyarrhythmia
- incidence rate and incidence rate ratio of bradycardia
- incidence rate and incidence rate ratio of cardiac fibrillation
- incidence rate and incidence rate ratio of cardiac flutter
- incidence rate and incidence rate ratio of tachyarrhythmia
- incidence rate and incidence rate ratio of atrial fibrillation
- incidence rate and incidence rate ratio of atrial flutter
- incidence rate and incidence rate ratio of cardiac arrest
- incidence rate and incidence rate ratio of torsade de pointes
- incidence rate and incidence rate ratio of ventricular arrhythmia
- incidence rate and incidence rate ratio of ventricular fibrillation
- incidence rate and incidence rate ratio of ventricular tachyarrhythmia
- incidence rate and incidence rate ratio of palpitations
- incidence rate and incidence rate ratio of chest pain
- incidence rate and incidence rate ratio of gait disturbances
- incidence rate and incidence rate ratio of injection site discomfort
- incidence rate and incidence rate ratio of injection site erythema
- incidence rate and incidence rate ratio of injection site irritation
- incidence rate and incidence rate ratio of injection site pain
- incidence rate and incidence rate ratio of stevens-johnson syndrome
- incidence rate and incidence rate ratio of toxic epidermal necrolysis
- incidence rate and incidence rate ratio of angioedema
- incidence rate and incidence rate ratio of urticaria

- incidence rate and incidence rate ratio of pruritus
- incidence rate and incidence rate ratio of rash
- incidence rate and incidence rate ratio of dizziness
- incidence rate and incidence rate ratio of somnolence
- incidence rate and incidence rate ratio of paresthesias
- incidence rate and incidence rate ratio of loss of consciousness
- incidence rate and incidence rate ratio of syncope
- incidence rate and incidence rate ratio of appetite disorder
- incidence rate and incidence rate ratio of decreased appetite

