Paraplegic gait (finding)	SCTID: 250035005
On examination - gait spastic (finding)	SCTID: 163685000
On examination - limping gait (finding)	SCTID: 163691003
Investigations	
ECG PR Prolonged	
Electrocardiogram: partial atrioventricular block - long PR (finding)	SCTID: 164902006
Prolonged PR interval (finding)	SCTID: 164947007
Injury, poisoning and procedural complications	
Injection site discomfort	
Injection site burning (disorder)	SCTID: 95389008
Injection site reaction (disorder)	SCTID: 95377006
Injection site disorder (disorder)	SCTID: 95376002

Table 3 SNOMED-CT concepts for the study	
Study outcome	SNOMED code
Injection site dermatitis (disorder)	SCTID: 95393002
Injection site urticaria (disorder)	SCTID: 95394008
Injection site edema (disorder)	SCTID: 95392007
Swelling at injection site (disorder)	SCTID: 213340005
Injection site inflammation (disorder)	SCTID: 95391000
Injection site induration (disorder)	SCTID: 95402002
Induration at injection site (disorder)	SCTID: 213337005
Injection site hypersensitivity (disorder)	SCTID: 95378001
Injection site cyst (disorder)	SCTID: 95396005
Injection site mass (disorder)	SCTID: 95395009
Injection site ulcer (disorder)	SCTID: 95400005
Injection site abscess (disorder)	SCTID: 95382004
Injection site atrophy (disorder)	SCTID: 95404001
Injection site necrosis (disorder)	SCTID: 95397001
Injection site fibrosis (disorder)	SCTID: 95403007
Injection site bruising (disorder)	SCTID: 95401009
Injection site infection (disorder)	SCTID: 95381006
Injection site granuloma (morphologic abnormality)	SCTID: 24389009
Injection site thrombosis (disorder)	SCTID: 95386001
Injection site hemorrhage (disorder)	SCTID: 95385002
Injection site paresthesia (disorder)	SCTID: 95399003
Injection site nerve damage (disorder)	SCTID: 95390004
Injection site malabsorption (disorder)	SCTID: 95387005
Injection site extravasation (disorder)	SCTID: 95384003
On examination - Injection sites abnormal (disorder)	SCTID: 308092004
Injection site sterile abscess (disorder)	SCTID: 95383009
Injection site pigmentation change (disorder)	SCTID: 95380007
Application AND/OR injection site disorder	SCTID: 95363008
Application site rash (disorder)	SCTID: 95371007
Injection site pain (disorder)	SCTID: 95388000
Erythema at injection site (disorder)	SCTID: 213338000
Injection site irritation (disorder)	SCTID: 95379009
Injection site erythema	

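### Injection-site outcomes, which are the whole Injury primary outcome, are divided by all follow-up days, so the rate does not describe IV exposure and the rate ratio depends on each group's IV share of follow-up

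*Protocol*

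**What the plan says.** Section 5.5.1 names this group as one of eleven primary outcomes: "The incidence rate and incidence rate ratio of injury, poisoning and procedural complications (selected PTs as described in Section 5.5.5". The list in section 4, repeated in 5.5.5, contains four terms and all are injection-site terms. The first is "Injection site discomfort"; the others are erythema, irritation and pain. Each is also a secondary outcome in 5.5.2, for example "incidence rate and incidence rate ratio of injection site pain". Under this heading Table 3 holds injection-site codes and a few broader ones such as "Application AND/OR injection site disorder".

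Section 5.9.1.2 gives one rule for all outcomes. For the events: "The numerator will be the total number of patients with the outcomes identified during the follow-up period". For the time: "The denominator will be in patient-days". The section speaks of days at risk, but then fixes what that means: "The person time for each patient will be calculated as the total number of days of follow-up as described in Section 5.3.3".

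Section 5.3.3 sets the follow-up:
- After one IV dose and a switch to oral lacosamide, "the follow up for AE evaluation will cease after a maximum of seven days of oral therapy". The same limit applies after one IV dose with no further lacosamide.
- After more than one IV dose and a switch to oral, follow-up may run to 37 days from the index date.
- In all cases it stops earlier at discharge, transfer out, death, or when another antiepileptic drug replaces or is added to lacosamide.

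**The concern.** A local reaction to IV lacosamide is tied to the period of IV administration and a short time after it. The protocol takes this view itself: 5.9.4 mentions injection-site irritation and pain when discussing immediate events, and expects most events within a day of IV dosing. Yet oral-only and lacosamide-free days enter the denominator of these outcomes on the same footing as IV days.

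Two things are at stake. First, the primary objective is to estimate incidence, and a reader will naturally take the injection-site rate as describing IV treatment, which it does not. Second, the rate ratio compares dose groups. If one group spends a larger part of its follow-up on IV treatment, the ratio reflects that difference as well as dose. Section 5.1 assumes that children given a loading dose are more likely to be in refractory status epilepticus, so a difference in IV duration, length of stay or time to another drug is plausible. These arise after the index date, so the baseline propensity score in 5.9.1.1 cannot balance them.

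**Working it through.** The protocol states no injection-site rate, IV duration or realised length of follow-up, so there is no figure to reproduce. The limits of 7 and 37 days come from 5.3.3. All IV durations and shorter follow-up times below are assumptions.

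**Dilution of the rate.** Suppose events are rare and all fall on IV days. With d IV days and F follow-up days per child, the rate per IV day divided by the rate per follow-up day is F/d.

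| IV days (d) | Follow-up days (F) | F/d |
|---|---|---|
| 1 | 1 | 1.0 |
| 1 | 3 | 3.0 |
| 1 | 7 | 7.0 |
| 2 | 37 | 18.5 |
| 3 | 3 | 1.0 |
| 3 | 7 | 2.3 |
| 3 | 14 | 4.7 |
| 3 | 37 | 12.3 |
| 5 | 10 | 2.0 |
| 5 | 37 | 7.4 |
| 10 | 14 | 1.4 |

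For a mixed cohort, half with one IV day and half with three, the mean is (1 + 3)/2 = 2 IV days. The factor is then:
- follow-up of 2 and 4 days: 3/2 = 1.5
- follow-up of 3 and 6 days: 4.5/2 = 2.25
- follow-up of 7 and 14 days: 10.5/2 = 5.25
- follow-up of 7 and 37 days: 22/2 = 11.0

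**Stopping the clock at the event.** Take 100 children, e events on day 1, one IV day and F = 7. The rate per follow-up day is e/(e + (100 − e) × 7), and the rate per IV day is e/100. For e = 1 the ratio is 0.0100/0.00144 = 6.9. For e = 20 it is 0.200/0.0345 = 5.8. Truncation changes little.

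**Allowing one extra day at risk.** The factor becomes F/(d + 1): 7/2 = 3.5 for one IV day followed for seven, 12/6 = 2.0 for five IV days followed for 12, and 37/6 = 6.2 for five followed for 37.

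**Rate ratio.** If the true ratio per IV day is 1, the ratio per follow-up day is (d/F in the high-dose group)/(d/F in the comparator).
- Equal shares, 3 of 10 days in both groups: 1.00.
- 1 of 7 days against 3 of 14: 0.143/0.214 = 0.67.
- 3 of 37 days against 3 of 14: 0.081/0.214 = 0.38. Exchanging the groups gives 37/14 = 2.64.
- One extra day at risk; single-dose children with 2 of 7 days and the rest with 6 of 12; 20% single-dose in the high-dose group and 60% in the comparator: (0.2 × 2 + 0.8 × 6)/(0.2 × 7 + 0.8 × 12) = 5.2/11.0 = 0.473, against (0.6 × 2 + 0.4 × 6)/(0.6 × 7 + 0.4 × 12) = 3.6/9.0 = 0.400. The ratio is 1.18.

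**Planned sensitivity analysis.** Section 5.9.1.4 drops the 30 days after IV lacosamide stops. If the clock then ends at the last IV dose, the factor is 1. If exposure is held to continue through the 7-day gap in 5.3.3, the factor can still be (1 + 7)/1 = 8 for one IV day and (3 + 7)/3 = 3.3 for three. The text does not say which applies.

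**The case against.** A reader might infer that the published rates will be several-fold too low. The documents do not support this. They give neither IV duration nor realised stay, and censoring at discharge or at another antiepileptic drug may end follow-up soon after the last IV dose. Three IV days with follow-up ending on day 3 to 7 give only 1.0 to 2.3. The day-37 cases need a child who stays in hospital throughout with no other such drug. That objection stands in full.

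A reader might also infer that days after IV dosing cannot yield an event. Table 3 says otherwise: it includes injection-site abscess, fibrosis and granuloma, which may be coded later. This stands too, and it argues against discarding later codes. Nor would a narrower window settle attribution: the codes do not name the drug or the line, and 7.4 says that product and event generally cannot be linked.

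The protocol also has partial safeguards. Section 5.9.1.2 warns that rates for early events or a falling hazard need caution, and a hazard that drops once IV dosing stops fits that warning. But the warning changes no denominator. The sensitivity analysis may or may not remove the dilution, as shown above. Counts and frequencies are planned for each group and largely supply the proportion affected, but the rate ratio still rests on person time.

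Finally, a rate per follow-up day is a legitimate, defined quantity, and bias in the rate ratio is not established: with equal IV shares there is none. Both points are right. What remains is that no main analysis matches this primary outcome to its period of exposure.

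**Conclusion.** The point holds in a limited form. For the Injury primary outcome and its four secondary components, 5.9.1.2 yields a rate per follow-up day that understates the rate during IV exposure whenever follow-up runs past IV dosing. The factor is not fixed by the documents. It is about 1 if follow-up ends with IV dosing and several-fold if it runs well beyond the last IV dose; the largest case computed is 18.5. These figures assume that events fall on IV days, and they shrink if a day after dosing counts as at risk or if some events are coded later.

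The rate ratio is distorted only if the IV share of follow-up differs between dose groups. Neither direction nor size can be known from the protocol; the illustrations run from 0.38 to 2.64 under a true ratio of 1. The issue is confined to one of eleven primary outcomes. It is worth correcting because the correction is cheap and makes that estimate interpretable.

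**What to change.** In 5.9.1.2, for the four injection-site outcomes and the Injury outcome:
- Add a rate and rate ratio over days with IV lacosamide plus a short prespecified window. The 24 hours named in the executive summary for the loading-dose assessment is a candidate; current 5.9.1.3 gives no window.
- Report the proportion of children affected beside it.
- Keep the all-follow-up rate, and list injection-site codes outside the window separately rather than dropping them.

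Two clarifications belong with this. Section 5.9.1.2 describes censoring as thirty days after IV lacosamide stops, while 5.3.3 sets a maximum of 37 days from index with censoring at discharge; these must be reconciled. Section 5.9.1.4 should state whether its shortened follow-up ends at the last IV dose or after the 7-day gap.

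The cost is a sentence or two, one further derived denominator and a footnote, since one outcome group would carry an additional denominator. Section 5.5.4 anticipates administration time stamps in most charts, but it also identifies lacosamide from prescription or dispensing data, with times only as available. Some children may therefore lack the times needed, and their number should be reported.

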### **5.9.1.3 Analysis of loading dose / higher than recommended initial IV LCM dose**

To examine safety and tolerability of iv LCM administration, the analysis of the key primary and secondary variables will be stratified by loading dose and recommended dose groups, stratified by ageband ie, separate tables per age band. Risk estimates will be provided with incidence rate ratios and 95% confidence limits.

### **5.9.1.4 Sensitivity Analysis**

Sensitivity analyses will be conducted to assess parameters used for defining the selection criteria, exposure, outcomes, and the study period as indicated below:

- Shorten the baseline period to 6 weeks
- The follow-up time will not include the 30 days after discontinuation of IV LCM
- Exclude patients with preexisting medical events of interest
- Outcome definitions will include a code for an outcome related medication/procedure within the period following the diagnosis record (to be defined)

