For both the higher IV LCM dose cohort and recommended initial/maintenance IV LCM dose comparator cohort, counts and frequencies of AEs will be reported, also the incidence rates of the AEs and associated 95% confidence intervals (CI) will be calculated. The numerator will be the total number of patients with the outcomes identified during the follow-up period. The denominator will be patient-days. Incidence rate ratios and associated 95% confidence intervals will be calculated for each outcome to compare the incidence rates of the AEs for the higher IV LCM cohort to those for the comparator cohort. To examine the safety and tolerability of increasing intravenous LCM loading dose a stratified analysis of the incidence of the primary and secondary variables will be conducted by increasing loading dose. Stratification will be centered around UCBs proposed recommended IV LCM loading dose.

If study numbers permit, all analyses will also be stratified by 1) exposure to additional AEDs, 2) IV LCM treatment indication, 3) preexisting medical events of interest, 4) use in the intensive care unit or other hospital departments, and 5) first time IV loading dose exposure vs multiple exposures. A number of sensitivity analyses will be conducted, these will include, 1) shortening the baseline period to 6 weeks, 2) excluding patients with preexisting medical events of interest, and 3) assessment of outcome definitions to assess the impact of the case definitions on the effect estimates.

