### 5.3.2 Baseline (pre-index) period

The baseline period for this study will be the 3 months prior to either the first newly initiated qualifying treatment episode of a higher IV LCM dose or a recommended initial IV LCM dose; for patients less than 3 months of age at index event, the baseline period will be birth through index event.

Data from the baseline period will be used to determine the indications for LCM and to define a new treatment episode. All available data prior to the index date will be used to evaluate the patient characteristics, diagnosis, procedures, and medications administered, dispensed or prescribed (AEDs, benzodiazepines and non-AEDs) medications, and identify preexisting

conditions of interest, if any. Preexisting medical events of interest are not exclusion criteria in this study; instead, they will be used to characterize the patient population. Section 5.5.6 details pre-existing medical events of interest that will be evaluated during the baseline period.

Potential indications for IV LCM include but are not limited to epilepsy, febrile seizures, and status epilepticus. The indications in both the higher and recommended IV LCM cohorts will be classified as follows:

- Patients with only one of the listed potential indications in the baseline period will be assigned the identified indication
- Patients with none of the listed potential indications in the baseline period will be classified as having other indications
- Patients with more than 1 of the listed potential indications in the baseline period will be classified as having multiple indications.

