### 5.5.3 Other variables - baseline characteristics

During the baseline period, patient characteristics (e.g. age at index date, gender, ethnicity, PEDSnet health system site, weight), clinical characteristics (i.e. number of previous AEDs and concomitant medications prescribed prior to the index date [AEDs, benzodiazepines and non-AEDs], prevalence of comorbidities, medical procedures such as EEG) will be evaluated. Baseline data will be assessed for IV LCM exposure indications, dosage of IV LCM and preexisting medical events of interest (i.e. cardiac conditions, dermatologic conditions, vascular conditions, injury, poisoning and procedural complications, general disorders and administration site conditions, investigations, drug reaction with eosinophilia and systemic symptoms syndrome, severe cutaneous adverse reactions, hypersensitivity events).

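### The pre-existing-event sensitivity analysis excludes a child for any of nine categories instead of for the outcome being analysed, and the list omits three primary outcomes

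*Protocol*

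**What the plan says.** Section 5.9.1.4 lists four sensitivity analyses. The third reads, in full, "Exclude patients with preexisting medical events of interest". The Executive Summary repeats it at patient level: "excluding patients with preexisting medical events of interest". Neither place ties the exclusion to a particular outcome.

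Section 5.5.3 closes the definition with a list: "preexisting medical events of interest (i.e. cardiac conditions, dermatologic conditions, vascular conditions, injury, poisoning and procedural complications, general disorders and administration site conditions, investigations", followed by "drug reaction with eosinophilia and systemic symptoms syndrome, severe cutaneous adverse reactions, hypersensitivity events". That makes nine categories. The propensity score covariates in 5.9.1.1 use the same list.

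Outcomes are analysed one at a time. Section 5.9.1.2 states: "Second, incidence rates for each of the following events will be calculated individually". Sections 5.9.1.2 and 5.9.1.5 then give a rate ratio for each outcome.

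Section 5.3.2 keeps children with pre-existing events in the main analysis. It gives two look-backs. One sentence says "All available data prior to the index date will be used to evaluate the patient characteristics" and goes on to cover pre-existing conditions of interest. Another refers to "pre-existing medical events of interest that will be evaluated during the baseline period", which is 3 months, or birth to index in the youngest children.

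**The concern.** Section 5.9.1.2 counts the first occurrence of an event after the index date, and children who already had the condition stay in. Table 3 includes codes for long-standing or past disease, such as chronic atrial fibrillation, chronic urticaria, and history of ventricular fibrillation or of palpitations. History of urticaria and of angina are marked there as prevalent codes; the ventricular fibrillation and palpitations terms are not. Old disease recorded again after index could therefore be counted as a new event.

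Section 5.1 says that baseline data serve, among other things, to identify prevalent cases. The exclusion in 5.9.1.4 is the natural check on whether such cases drive a rate ratio. For that purpose it should remove, for each outcome, the children who already had that outcome. As worded, it removes children for history unrelated to the outcome, and for three primary outcomes it is not aimed at prevalent cases at all. If a rate ratio then moves, the reader cannot tell whether this reflects the removal of prevalent cases or the removal of children with other illnesses.

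**Working it through.** The protocol gives no prevalence, retained number or expected effect for this analysis, so there is no figure to reproduce. The first two steps need no assumptions.

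**Step 1: the list against the outcomes.** Section 5.5.1 names 11 primary outcome categories.

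- On the 5.5.3 list: cardiac, skin (as dermatologic), injury and procedural, general and administration site, investigations, DRESS, severe cutaneous reactions, hypersensitivity. That is 8.
- Primary outcomes not on the list: nervous system, metabolism and nutrition, psychiatric. That is 3, and 8 + 3 = 11.
- On the list but not an outcome: vascular conditions. That is 1, and 8 + 1 = 9.

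**Step 2: what the rule removes.**

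- For a listed outcome, a child with a prior event of that outcome also has an event in at least one of the nine categories. The children kept by the any-of-nine rule are therefore a subset of those kept by matched exclusion. The any-of-nine rule can never keep more, whatever the prevalences or overlap. Any further children it removes have only unrelated history.
- For the three unlisted outcomes, a child with a prior event of the outcome stays in unless some other, listed history removes the child. Children without a prior event of the outcome are removed for unrelated history.

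**Step 3: how many children could be lost (assumed prevalences).** Suppose each category is present before index in a share p of children. With nine independent categories, the share kept is (1 − p)^9. Exclusion matched to one category keeps 1 − p. If all nine categories fell on the same children, the any-of-nine rule would also keep 1 − p.

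| p per category | Any of nine, independent | Matched to outcome (also any of nine, full overlap) |
|---|---|---|
| 1% | 0.99^9 = 91% | 99% |
| 5% | 0.95^9 = 63% | 95% |
| 10% | 0.90^9 = 39% | 90% |
| 20% | 0.80^9 = 13% | 80% |

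Half are kept when p = 1 − 0.5^(1/9) = 7.4%. Under independence, a minority is kept only above that value.

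Equal prevalence is a simplification. As an unequal example, in the order of the 5.5.3 list, assume 10%, 10%, 5%, 10%, 10%, 3%, 0.1%, 0.2% and 5%. The product of the nine (1 − p) terms is 57%. With no overlap the share kept is 1 − 0.533 = 47%; with full overlap it is 1 − 0.10 = 90%.

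Some overlap is built in. In Table 3 the DRESS code stands under DRESS, severe cutaneous reactions and hypersensitivity, and the Stevens-Johnson and toxic epidermal necrolysis codes stand under both skin disorders and severe cutaneous reactions.

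**The case against.** The strongest reply is that the any-outcome reading is inferred. A one-line bullet does not say that a child leaves every analysis, 5.9.1.2 works outcome by outcome, and a statistical analysis plan, which is not at hand, could apply the exclusion per outcome. It is true that programming detail may sit elsewhere. But the rule is stated twice at patient level, its key term is closed by a fixed list, and that list cannot give a matched exclusion for three of the 11 outcomes. The outcome-definition bullet in the same section is marked as still to be defined; this one is not.

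A second reply is that 5.9.1.4 gives its own purpose, which includes testing the selection criteria. Keeping children with pre-existing events is a selection choice, and reversing it at patient level tests that choice directly. This stands: the analysis is coherent as a test of that choice. It still does not isolate prevalent cases of the outcome analysed. A changed population is inherent in any restriction and is not itself an error.

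Third, a reader might infer that the rule leaves only a minority of the cohort. The documents do not support that. It rests wholly on assumed prevalences and on independence, which Table 3 contradicts. Several categories are also narrow when read as events of interest: injury is injection-site terms, investigations is PR prolongation, and general disorders is chest pain and gait.

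Fourth, a reader might infer that children with long records are selectively removed. That follows only if all prior data are used; under the baseline-period reading it largely disappears.

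Finally, pre-existing events also enter the propensity model, and 5.9 stratifies by them (the Executive Summary adds: if numbers permit). These lessen the dependence on this one analysis, but they use the same term, so they do not supply the missing outcome match.

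**Conclusion.** The point holds as a defect in one of four sensitivity analyses. Read as written, the exclusion is not tied to the outcome. For the eight listed outcomes it removes at least as many children as a matched exclusion, including some with only unrelated history. For nervous system, metabolism and nutrition, and psychiatric disorders it removes children for unrelated history and does not target prevalent cases. These statements follow from the text alone.

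The loss of children cannot be sized from the protocol. The range of 91% to 13% kept is illustrative and assumes equal, independent categories at 1% to 20% each. The main incidence rate ratios keep all these children and are not affected. The change is worth making before analysis, but nothing here undermines the primary comparison.

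**What to change.** Reword the bullet in 5.9.1.4, and align the Executive Summary with it:

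*For each outcome, exclude children with a record of that same outcome category before the index dose (for PR prolongation, also prior AV block); they remain in the analysis of all other outcomes.*

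The bracket is needed because PR prolongation sits under investigations and AV block under cardiac disorders, while one of the PR codes in Table 3 is itself a partial AV block finding.

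In the same edit:

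- apply the rule to all 11 primary outcome categories, which adds nervous system, metabolism and nutrition, and psychiatric disorders to the baseline definitions;
- state one look-back in 5.3.2 and use it here;
- re-estimate the propensity weights in each reduced set;
- report the number excluded by dose group for each outcome.

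The cost is a short text change, baseline flags for three more categories and some extra programming, since weights are refitted up to 11 times for the primary outcomes. No new data source is needed. The drawback is that the analysis set differs by outcome, so each table needs its own N.
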